### **Specimen Shipment**

Specimens will be shipped using Federal Express in insulated and refrigerated specimen boxes.

## **STUDY SCHEDULE**

### **Screening**

Before admission to the NIH Clinical Center to start therapy, patients will undergo an evaluation for eligibility in this protocol. During the eligibility evaluation, patients will undergo a thorough explanation of this protocol, be provided this protocol's consent for review, and be given multiple opportunities to ask questions about this study. This will be documented in the patient's chart. Female subjects of reproductive potential and male subjects with female partners of reproductive potential will be informed and educated that two reliable forms of contraception as described in the exclusion criteria from the start of the study until 6 months from the end of lonafarnib, ritonavir and lambda dosing must be utilized. Women will be instructed that they may not breastfeed during their participation in this study.

After signing consent, patients will begin screening for the study. Results for labs drawn within the prior six months may be used to determine eligibility. Screening will include:

- History and physical
- Review of concomitant medications
- Blood draw to include:
  - Hepatic panel
  - Mineral panel

3. PT/INR
4. AFP
5. Anti-HDV
6. HDV RNA
7. HDV and HBV genotyping
8. HCV RNA
9. Pregnancy test
10. ANA, ASMA, AMA, ceruloplasmin, ferritin, alpha 1 antitrypsin.
11. Ultrasound and Fibroscan
12. EKG
13. Anti-HIV 1/2
14. Lipid panel

**Baseline Evaluation and Initiation of Treatment (within 6 months of screening)**

If found to be eligible, the patient will be admitted to the NIH Clinical Center and undergo the following evaluation shortly before starting therapy.

If the patient was on HBV therapy prior to consenting to the study, they will continue on treatment for HBV. If the patient was not on HBV therapy, they will start on approved nucleos(t)ide treatment for a sufficient period of time prior to starting study medication in order for to demonstrate adequate suppression of HBV (serum HBV DNA of <2000 IU/mL).

Upon admission the patient will undergo the following:

1. Continuation of HBV therapy
2. MD Visit
3. Routine labs
4. Baseline labs
5. Pancreatic labs
6. Monthly labs
7. Reproductive labs
8. Serology panel
9. Immunological studies
10. Viral kinetics, pharmacokinetics
11. Microbiome studies
12. EKG

13. Ophthalmology, reproductive endocrine/urology, and nutrition consults (can occur prior to admission per patient's preference)
14. MRI
15. Fibroscan
16. Liver biopsy with hepatic venous pressure gradient measurements prior to starting therapy

### **Initiation of Treatment**

All patients will be initiated on lonafarnib 50 mg orally twice daily, ritonavir 100 mg orally twice daily and lambda 180 mcg subcutaneously weekly. Eiger BioPharmaceuticals, Inc will supply the lonafarnib, ritonavir and lambda interferon under a clinical trials agreement. Patients will be initiated on therapy one or two days after the liver biopsy and will remain in the clinical center for 72 hours after induction of therapy for observation of side effects, administration of medication, and timed blood draws to facilitate analysis of virological response kinetics and pharmacokinetic analysis. During the admission, frequent blood sampling will be performed (0, 6, 12, 18, 24, 36, 48 and 72 hours after, the first dose) for viral kinetics, pharmacokinetics and storage.

### **Monitoring on Therapy**

After induction of therapy, and completion of the inpatient stay as described above, patients will be treated as outpatients and followed on a regular basis in the outpatient clinic at the NIH Clinical Center.

### **Treatment Weeks 1, 2 and 3 (+/- 3 days)**

Patients will be scheduled as outpatients to undergo the following:

1. Continuation of HBV therapy
2. MD visit
3. Monitoring of vital signs and weight (>10% weight loss from baseline would result in a follow-up nutrition consult).
4. Routine labs
5. Pancreatic labs
6. Serology
7. Viral kinetics, pharmacokinetics and storage
8. EKG

### **Treatment Weeks 4, 8, 12, 16 and 20 (+/- 3 days)**

Patients will undergo the following as outpatients:

1. Continuation of HBV therapy
2. Continuation of study medication

3. MD Visit
4. Monitoring of vital signs and weight (>10% weight loss from baseline would result in a follow-up nutrition consult).
5. Routine labs
6. Pancreatic labs
7. Serology
8. Monthly labs
9. Reproductive labs
10. Immunological testing
11. Viral kinetics, pharmacokinetics and blood draw for storage
12. Microbiome studies
13. EKG

### **End of Therapy**

At the end of therapy (week 24), patients will be seen at the NIH Clinical Center for an evaluation as follows:

1. Continuation of HBV therapy
2. Discontinuation of study therapy
3. MD Visit
4. Monitoring of vital signs and weight (>10% weight loss from baseline would result in a follow-up nutrition consult).
5. Routine labs
6. Pancreatic labs
7. Serology
8. Baseline labs
9. Monthly labs
10. Consults
11. Reproductive labs
12. Immunological testing
13. Viral kinetics, pharmacokinetics and blood for storage
14. Microbiome
15. Imaging
16. Fibroscan
17. EKG

**Post Treatment Monitoring**

Patients will return for outpatient visits per the following schedule. As interferon alpha is the only recommended therapy for HDV, if a patient has been previously treated with interferon, there is no additional therapy to be offered. It is not planned to routinely offer interferon alpha to all patients after participating in this study. However, if a prolonged HDV flare with significant liver damage is demonstrated, rescue therapy with interferon alpha will be offered. Patients failing experimental therapy will not be excluded from therapy with standard interferon alpha.

**Post Treatment Weeks 1 and 2 (+/- 3 Days)**

After discontinuation of therapy at week 24, patients will be monitored on an outpatient basis and followed off-therapy for follow-up and blood testing:

1. Continuation of HBV therapy
2. MD Visit
3. Monitoring of vital signs and weight
4. Routine labs
5. Serology panel
6. Viral kinetics, pharmacokinetics and blood for storage

**Post Treatment Weeks 4, 8, 12, 16, 20 (+/- 5 days)**

1. Continuation of HBV therapy
2. MD Visit
3. Monitoring of vital signs and weight
4. Routine labs
5. Serology Panel
6. Monthly labs
7. Reproductive labs
8. Immunological testing (weeks 4, 8 and 16)
9. Viral kinetics, pharmacokinetics and blood for storage
10. Microbiome studies (window for microbiome is +/- 5 days)

**Post Treatment Week 24**

At the end of study followup (week 24 post treatment), patients will be readmitted to the NIH Clinical Center for an evaluation as follows:

1. Continuation of HBV therapy
2. MD Visit

3. Monitoring of vital signs and weight (>10% weight loss from baseline would result in a follow-up nutrition consult).
4. Routine labs
5. Pancreatic labs
6. Serology
7. Baseline labs
8. Monthly labs
9. Consults
10. Reproductive labs
11. Immunological testing
12. Viral kinetics, pharmacokinetics and blood for storage
13. Microbiome
14. Imaging
15. Fibroscan
16. EKG
17. Liver biopsy

### **Unscheduled Visits**

Data from unscheduled visits may be used in the study analysis. Unscheduled visits may occur due to the development of unexpected symptoms, laboratory abnormalities, or side effects which may require clinical follow-up outside of the scheduled visits. Additional evaluations, including laboratory, radiologic and EKG evaluations may be performed based on presenting symptoms or clinical suspicion.

### **Remote Visits**

In the event that circumstances beyond our control preclude the travel of one or more of the study participants to the NIH Clinical Center for a visit, or otherwise would put their health at greater risk (i.e. epidemic or pandemic), we will endeavor to establish capabilities for remote visits. Specifically, for safety visits, the study team will arrange for local laboratory studies to be done, which include comprehensive metabolic panel, Liver function tests (including Tbili, AST and ALT), CBC with diff, PT/INR, HBV DNA quantitative and HDV quantitative measurements and conduct a telehealth visit with the patient. This telehealth visit will adhere to HHS guidance (<https://www.hhs.gov/hipaa/for-professionals/special-topics/emergency-preparedness/notification-enforcement-discretion-telehealth/index.html>) and can use all telehealth modalities under the good faith provision during a pandemic/epidemic as allowed by HHS for care of study participants. Unscheduled visits, due to safety, may also be conducted remotely through telehealth and/or offsite laboratory and radiologic studies and/or in conjunction with a local physician with the supervision of the study PI. The laboratory studies will be performed through Quest or LabCorp or with the local physician, and results will be sent to the study team for safety monitoring and

oversight. Radiology studies, when needed, will be arranged through a local, non-study physician, or directly by the study team, at a site close to the participants home area if travel to the NIH is not possible. As per FDA guidance, The study team will attempt to collect research blood at these visits to be sent to the NIH Clinical Center when possible, to address study outcome measures. During a pandemic affecting patient travel, serial missed research collections will not be considered major study deviations and will be reported to the IRB at the time of continuing review.

#### **Monitoring of Patients Discontinuing Therapy**

Therapy will be stopped for intolerance to lonafarnib, ritonavir and/or lambda (which is carefully defined in table 4). Patients who stop therapy due to intolerance, withdraw because of an adverse event, self-discontinue therapy or drop out from the study will be considered as treatment failures. Patients in whom therapy is stopped early or who discontinue treatment on their own will initially be followed in the same manner as those who do not respond as defined in the protocol. After treatment is discontinued, the patient will be followed for at least 24 weeks with visits to the outpatient clinic as per the post-treatment monitoring schedule described above. Thereafter, patients may be followed on an unscheduled basis under protocol 91-DK-0214 as is typical for patients who have participated in studies done by the Liver Diseases Branch.

**Table 1: Study Design**

			Day 0	Study Weeks (+/- 3 days)				Study Weeks (+/-5 days)	
	Study Week/Procedures	Baseline Evaluation	Start Treatment	1, 2, 3	4, 8, 12, 16, 20	24	25, 26	31 28, 32, 36, 40, 44	48
Lonafarnib, Ritonavir, Lambda	HDV Therapy		x	x	x	x			
HBV Flare Prophylaxis	HBV Therapy	x	x	x	x	x	x	x	X
H&P	MD Visit	x		x	x	x	x	x	X
Vital signs									
Review of symptoms									
Concomitant meds									
Symptom Questionnaire									
Review of medication compliance									
CBC + diff	Routine labs	x		x	x	x	x	x	X
acute									
mineral									
lipid									
hepatic									
LDH									
CK									
Serum uric acid									
total protein									
amylase	Pancreatic labs	x		x	x	x			X
lipase									
HBsAg	Serology Panel	x		x	x	x	x	x	X
anti-HBs									
HBeAg									
anti-Hbe									
PT/INR	Baseline Labs	x				x			X
PTT									
Reticulocyte count									
Plasma Haptoglobin									
anti Hbc									
PT	Monthly labs	x			x	x		x	X
Thyroid panel									
Pregnancy test									
Ophthalmology exam	Consults	x				x			X
Reproductive consult									
LH	Reproductive labs - Females	x			x	x		28, 32, 36	X
FSH									
estradiol									
Progesterone									
AMH									
DHEA									
DHEAS									
Androstenedione									

Testosterone									
Free testosterone									
SHBG									
17-OHP									
Inhibin B	Reproductive labs - Males	x			x	x		28, 32, 36	X
LH									
FSH									
Free testosterone									
total testosterone									
30-50 mL serum for immunology.	Immunological Testing	x	0, 24 hours		4, 8, 12	x		28, 32, 36	X
10 mL red top for PK	VK, PK and Storage		0, 6, 12, 18, 24, 36, 48, 72 hours	x	x	x	x	x	X
HBV DNA									
HDV RNA									
7 mL whole blood for storage									
Blood	Microbiome Studies	x			x	x		x	X
Stool									
Dietary questionnaire									
MRI	Imaging	X				x			X
Ultrasound									
Fibroscan									
EKG	EKG	x		x	x	x			X
Transjugular liver biopsy with portal pressure measurements or percutaneous liver biopsy	Liver Biopsy	x							X

### Fecal microbiome and Bacterial Translocation (BT) analysis

With the recent introduction of highly sensitive analytical methods, the ability to meticulously describe the intestinal microbiome in health and disease has allowed for identification of fecal microbial dysbiosis. More recently, investigators have begun evaluating associations between the fecal microbiome and bacterial translocation in chronic liver disease, advanced liver disease and its potential contribution in poor outcomes in liver disease.

In this study, for research related purposes, we plan to utilize pyro-sequencing techniques to survey microbial diversity in patients' fecal samples. Patients may refuse the microbiome portion of the study and still participate in other portions of this study. Prior to stool sample collection, all the patients will continue their routine diets. At each visit, a specific medication history (including prescription and OTC medications) and dietary recordings (appendix 2) will be taken. Samples (stool and serum) will be elicited at the time points shown in Table 2 and stored in -80C for future analysis.

At the time of analysis, we intend to evaluate the relationship between specific microbiome maps and the occurrence of BT. In addition, species homology between blood and fecal samples will be determined by deep sequencing.

Bacterial DNA will be extracted from patient serum and stool using QIAamp DNA mini kit (Qiagen) according to the manufacturer's protocol. Patients' dietary history of the day prior to stool sample collection and any changes made in medication use since screening visit will be recorded. Polymerase chain reaction (PCR) for a conserved region of the 16S rRNA gene will be performed with two universal primers, forward primers (27F-Bac, 5'-AGAGTTTGTATCMTGGCTCAG-3') and reverse primers (543R-Bac, 5'-ATTACCGCGGCTGCTGGC-3') to detect and identify the bacterial DNA. For each sample, uniquely barcoded universal primers will be used for multiplexing. Amplified PCR products will be analyzed by agarose gel electrophoresis and then be pooled for pyrosequencing. Amplicons will undergo deep sequencing to be performed at SAIC-Frederick Inc. Sequences with a minimum length of 200 bp will be analyzed using mothur (version 1.21.0) for 16S rRNA gene sequence analysis. Taxonomic classification will be done using the RDP Classifier and phylogenetic tree will be generated using the Clearcut program. Stool samples will be collected at the beginning of study, every 4 weeks, at the end of treatment week 24 and every 4 weeks of post treatment. (Table 2)

Blood will be drawn and used to measure microbial cell wall products, (LPS, peptidoglycan and beta-D-glucan), host response markers and selected cytokines. This blood samples will be collected whenever we collect the stool sample. (Table 2).

**Table 2. Time points for collection of samples for Microbiome & Bacterial Translocation Analysis**

Time	Therapy	Blood and stool sample for bacterial translocation and blood sample for cytokines
Baseline Time = -2 to 0	None	*
On Tx Week 4,8,12,16,20	Lonafarnib/Ritonavir and lambda IFN	*
End of Tx Week 24	Lonafarnib/Ritonavir and lambda IFN	*
Post Tx week 4, 8,12, 16, 20, 24	None	*

An acceptable deviation for collection of these samples is +/- 5 days.

All microbiome related testing is intended for research purposes.

### **Immunologic Analysis**

Chronic delta hepatitis is characterized by a lymphomononuclear infiltrate of the liver. The relative composition of this cellular infiltrate (HDV-specific T cells versus HBV-specific T cells versus nonspecific bystander cells), the antigenic targets within HDV that

are recognized by these T cells and the contribution of the HDV-specific T cell response to disease progression are not known.

We aim to define the HDV-specific T cell response in blood samples of HDV/HBV-coinfected patients in the chronic stage of disease prior to treatment. Peripheral blood mononuclear cells (PBMC) will be isolated from blood samples. The HDV-specific CD4 and CD8 T cell response to recombinant delta antigen will be assessed by measuring cytokines (IFN $\gamma$ , TNF $\alpha$ , IL-2) by multicolor flow cytometry and enzyme-linked immunospot assays. Individual responses will be mapped with 41 overlapping peptides spanning the delta antigen and minimal optimal epitopes will be defined. The quality and strength of the HDV-specific T cell response will be compared to the quality and strength of the HBV core and surface antigen-specific response.

We also plan to take advantage of the fact that the prenylation inhibitor is a potent antiviral drug with no direct effect on the immune system. We will also evaluate whether a reduction of HDV viral or antigen load determined by treatment with the prenylation inhibitor causes a qualitative or quantitative change of the T cell response in the peripheral blood, and specifically, the emergence of HDV-specific memory T cells that we have identified in a rare case of a patient who spontaneously recovered from HDV infection ([name], [name], unpublished).

### **Design of the Trial/Statistical considerations**

This study is designed as a phase 2a FDA regulated clinical study evaluating the utility of combination triple therapy of lonafarnib, ritonavir and lambda interferon in patients with chronic HDV infection. This study should show if HDV suppression is possible; assist in suggesting if this dose is effective for viral suppression; and how well lonafarnib, ritonavir and lambda interferon are tolerated. Thus, assessment of virologic response is the primary therapeutic endpoint and safety/tolerability is the primary safety endpoint.

Measurement of HDV RNA levels will be performed in two batches, the first batch will be analysed after the last patient has completed treatment, and the second batch when the last patient completes post-therapy follow-up.

In order to achieve a primary virologic response goal of a 2-log decline in HDV RNA in serum at end of 24 weeks of therapy, a total of 26 patients will be enrolled. This designation was made based on a power calculation with a statistical power designated at 0.9, alpha at 0.05, and two tailed testing, the effect size was found to be -1.1.

$$effect\ size = \frac{2672.231 - 267223.1}{240500.8} = -1.1$$

Based off prior interferon based studies, we would also include a potential drop out rate of 30%. Thus, the sample size desired will be 26 subjects.

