### **ASSESSMENT OF RESPONSE TO THERAPY**

#### **Primary Therapeutic End Point:**

Decrease of HDV RNA by >2 log from baseline at 24 weeks of therapy with lonafarnib plus ritonavir and lambda interferon.

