## **STUDY PROCEDURES AND SCHEDULE**

This is an open-label clinical trial treating 26 adult patients with chronic delta hepatitis with lonafarnib plus ritonavir and lambda interferon for 24 weeks. Patients will undergo baseline testing including blood draws, imaging, safety consults, and liver biopsy with portal pressure measurements prior to starting therapy. During therapy, all patients will be monitored with quantitative HDV RNA and HBV DNA levels as well as routine safety measures and liver function tests. After 24 weeks, therapy will be stopped and patients will again undergo repeated testing including blood draws, imaging, and safety consults. After stopping therapy, patients will be followed for an additional 24 weeks. At the end of the 24 weeks of post-therapy follow-up, patients will be re-admitted to the NIH Clinical Center and will undergo repeat testing including blood draws, imaging, as well as a transjugular liver biopsy with hepatic venous pressure gradient measurements.

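### The 26 patients match one arm of a two-group comparison, but the trial measures one group twice, so the stated 0.90 power is not the power of this design

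*Combined protocol and SAP*

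**What the plan says.** Under Study Procedures and Schedule the protocol describes one treated group: "This is an open-label clinical trial treating 26 adult patients with chronic delta hepatitis". No control or comparison group appears anywhere. The Primary Therapeutic End Point is "Decrease of HDV RNA by >2 log from baseline at 24 weeks of therapy", so each patient is compared with their own baseline.

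The sample size is justified in Design of the Trial/Statistical considerations, which reports a "power calculation with a statistical power designated at 0.9, alpha at 0.05, and two tailed testing, the effect size was found to be -1.1". The effect size is a difference of two values, 2672.231 minus 267223.1, divided by 240500.8. The section then continues: "we would also include a potential drop out rate of 30%. Thus, the sample size desired will be 26 subjects".

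That section does not name the test, the number of evaluable patients before dropout, what 240500.8 is the SD of, or a correlation between baseline and week 24.

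**The concern.** Baseline and week-24 values from the same patients are paired, and the power of a paired comparison depends on the SD of the within-patient change. The plan's inputs lead to 26 when they are put into the formula for two separate groups and only one group's size is kept. In that reading, 0.90 is the power of a trial with a second group of the same size, which does not exist here.

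This section is the only justification for the enrolment target. If its power figure belongs to another design, a reader cannot tell what change the trial can detect, and the sponsor has no stated basis for choosing the analysis or judging the effect of extra dropout.

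**Working it through.** **Inputs**, all from Design of the Trial/Statistical considerations: power 0.9, two-sided alpha 0.05, dropout 30%, stated total 26. Effect size: (2672.231 − 267223.1)/240500.8 = −1.100. The week-24 value is 1% of the baseline value, which is a 2-log fall. The divisor is 90% of the baseline value.

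**Step 1. Reproduce 26.** Two independent groups, normal approximation, per arm:

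n = 2 × (1.960 + 1.282)² / 1.1² = 2 × 10.507 / 1.21 = 17.4, so 18.

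18 / 0.70 = 25.7, so **26**. This is the stated figure, but it is the size of one arm. Both arms together would be 36 before dropout and 52 after.

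The exact t calculation gives 19 per arm (18 per arm has power 0.894). That leads to 28 by 19/0.70, or 25 by 19 × 1.3, so the exact match depends on the normal approximation.

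**Step 2. Same inputs, paired design**, taking 1.1 as mean change divided by the SD of the change.

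- Normal approximation: 10.507 / 1.21 = 8.7, so 9 completers; 9/0.70 = 12.9, so 13 enrolled.
- Paired t-test: power 0.871 at n = 10 and 0.907 at n = 11, so 11 completers; 11/0.70 = 15.7, so **16** enrolled.

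**Step 3. Power of the paired design at the planned size.** Expected completers: 26 × 0.70 = 18.2, so 18. Paired t-test power at a standardised change of 1.1 is **0.992** with 18 and above 0.999 with 26. The standardised change detectable with 0.90 power is 0.81 with 18 and 0.66 with 26.

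**Step 4. If 240500.8 is instead a single-visit SD.** Assume it is equal at both visits, with within-patient correlation ρ. Neither assumption is in the documents. The standardised change is then 1.1/√(2(1 − ρ)).

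| ρ | Standardised change | Paired t power, 18 completers | Completers for 0.90 | Enrolled (÷ 0.70) |
|---|---|---|---|---|
| 0 | 0.778 | 0.875 | 20 | 29 |
| 0.1 | 0.820 | 0.906 | 18 | 26 |
| 0.3 | 0.930 | 0.960 | 15 | 22 |
| 0.5 | 1.100 | 0.992 | 11 | 16 |
| 0.7 | 1.420 | above 0.999 | 8 | 12 |

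At ρ = 0, two other routes also give 26: the normal approximation (18, then 18/0.70) and the t calculation with dropout added as 20 × 1.3.

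**Step 5. Is the equal-SD assumption plausible?** 240500.8 / 2672.231 = 90, so equal SDs would put the week-24 SD at 90 times the week-24 mean. If the week-24 SD shrinks with the mean to about 1% of the baseline SD (also an assumption), the SD of the change is √(1 + 0.01² − 2ρ × 0.01) times the baseline SD. For ρ from 0 to 1 that factor runs from 1.000 to 0.990, and the standardised change from 1.10 to 1.11. Power at 18 completers then stays near 0.99 almost whatever the correlation.

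**The case against.** The strongest reply is that the number 26 cannot prove which formula was used. With equal SDs and no correlation, the paired normal formula is algebraically the same as the two-group per-arm formula. With a correlation of 0 to 0.1, paired power at 18 completers is 0.875 to 0.906, close to the stated 0.90. The two-group match is itself sensitive to using the normal approximation. All of that stands. A reader might infer that 26 can come only from a two-group calculation; the documents do not support that, and the method remains an inference.

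The reply does not rescue the stated power, though. It needs two unstated assumptions, and the plan's own figures make the equal-SD one implausible (Step 5).

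A second reply is that no harm follows, since 26 exceeds the 16 a paired t-test would need. This is right as to direction. It limits the point to a wrong justification.

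A third is that a paired test of mean change does not settle the section. The effect size is on raw IU/mL while the goal is in logs, and the primary endpoint can be read as a per-patient response. This also stands, and it shapes the fix.

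**Conclusion.** The point holds as a fault of justification. The stated 26 matches one arm of a two-independent-group comparison, while the trial is one group measured at baseline and week 24. If 1.1 is the standardised within-patient change, 0.90 power needs 11 completers and 16 enrolled, and the planned 18 completers have about 0.99 power. If 240500.8 is an SD common to both visits, power at 18 completers runs from 0.875 to above 0.999 for correlations of 0 to 0.7. The low end rests on a spread at week 24 that the plan's own means make implausible.

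Three stronger conclusions might be inferred and are not supported:

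- **That the trial is underpowered for a mean change.** On the plan's inputs the error runs the other way, to a larger trial than a paired test needs.
- **That the data will be analysed as two independent groups**, with a distorted error rate. The plan names no test and proposes no such analysis.
- **That a paired test on log10 change has 0.99 power.** The 1.1 is a raw-scale figure, and the documents give no SD of log10 change.

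**What to change.** Keep 26. In Design of the Trial/Statistical considerations, replace the power statement with one for a single group measured twice:

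1. Name a paired test on within-patient change in log10 HDV RNA from baseline to week 24.
2. Define the effect size as the mean change divided by the SD of the within-patient change, and state that SD with its source.
3. State what the trial can detect. Suggested wording: *With 18 completers of 26 enrolled, a paired t-test at two-sided 0.05 has 0.90 power for a mean change of 0.81 SDs of the within-patient change.*
4. Recompute once the log10 SD is supplied, and do not quote 0.99 before then. As a guide, for a mean fall of 2 log10 tested against no change, 0.90 power holds while that SD is at most 2/0.811 = 2.5 log10.
5. If the primary endpoint is a per-patient response of more than 2 logs, add the precision of that proportion. Monitoring of Patients Discontinuing Therapy counts dropouts as treatment failures, so the denominator is all 26. By the normal approximation, the 95% half-width at an assumed response of 50% is 1.96 × √(0.25/26) = 0.19.

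The cost is a few sentences and one SD that the sponsor must find and justify. Enrolment, visits and assays do not change.
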